7.1.2. Analytical Methodology

Plasma concentrations of rosuvastatin and sotorasib will be determined using validated analytical procedures. Specifics of the analytical method will be provided in a separate document.

7.2. Safety and Tolerability Assessments

7.2.1. Adverse Events and Serious Adverse Events: Time Period and Frequency for Collecting and Reporting Safety Event Information

Adverse event definitions, assignment of severity and causality, and procedures for reporting Adverse Events and Serious Adverse Events are detailed in [Appendix 1](#).

The condition of each subject will be monitored from the time of signing the ICF to EOS. Subjects will be observed for any signs or symptoms and asked about their condition by open questioning, such as “How have you been feeling since you were last asked?”, at least once each day while resident at the study site and at each study visit. Subjects will also be encouraged to spontaneously report Adverse Events and Serious Adverse Events occurring at any other time during the study.

Adverse Events

The adverse event grading scale to be used in this study is described in [Appendix 1](#).

The Investigator is responsible for ensuring that all non-serious adverse events observed by the Investigator or reported by the subject (whether reported by the subject voluntarily or upon

questioning, or noted on physical examination) from enrollment through the EOS are recorded/reported using the appropriate eCRF.

Serious Adverse Events

The Investigator is responsible for ensuring that all serious adverse events observed by the Investigator or reported by the subject that occur after signing of the ICF through 30 days after the last dose of study treatment or the EOS visit (whichever is later) are reported using the appropriate eCRF and reported on the paper-based Serious Adverse Event Report Form (described in [Appendix 1](#)).

All serious adverse events will be collected, recorded, and reported to the Sponsor within 24 hours of the Investigator's knowledge of the event. The Investigator will submit any updated serious adverse event data to the Sponsor within 24 hours of it being available.

The criteria for Grade 4 in the Common Terminology Criteria for Adverse Events grading scale differs from the regulatory criteria for serious adverse events. It is left to the Investigator's judgment to report these Grade 4 abnormalities as serious adverse events.

Serious Adverse Events After the Protocol-required Reporting Period

There is no requirement to monitor study subjects for serious adverse events following the protocol-required reporting period or after EOS. However, these serious adverse events should be reported to Amgen (regardless of causality) if the Investigator becomes aware of them. Per local requirements in some countries, Investigators are required to report serious adverse events that they become aware of after EOS. If serious adverse events are reported, the Investigator is to report them to the Sponsor within 24 hours following the Investigator's knowledge/awareness of the event using the paper-based Serious Adverse Event Report Form.

Serious adverse events reported outside of the protocol-required reporting period will be captured within the Sponsor's safety database as clinical trial cases and handled accordingly based on relationship to investigational product.

Method of Detecting Adverse Events and Serious Adverse Events

Care will be taken not to introduce bias when detecting adverse events and/or serious adverse events. Open-ended and non-leading verbal questioning of the subject is the preferred method to inquire about adverse event occurrence.

Follow-up of Adverse Events and Serious Adverse Events

After the initial adverse event/serious adverse event report, the Investigator is required to proactively follow each subject at subsequent visits/contacts. All adverse events and serious adverse events will be followed, where possible, until resolution, stabilization, until the event is

otherwise explained, or the subject is lost to follow-up. This will be completed at the Investigator's (or designee's) discretion.

All new information for previously reported serious adverse events must be sent to Amgen within 24 hours following knowledge of the new information. If specifically requested, the Investigator may need to provide additional follow-up information, such as discharge summaries, medical records, or extracts from the medical records. Information provided about the serious adverse event must be consistent with that recorded on the eCRF.

Regulatory Reporting Requirements for Serious Adverse Events

If subject is permanently withdrawn from protocol-required therapies because of a serious adverse event, this information must be submitted to the Sponsor.

Prompt notification by the Investigator to the Sponsor of serious adverse events is essential so that legal obligations and ethical responsibilities toward the safety of subjects and the safety of a study treatment under clinical investigation are met.

The Sponsor has a legal responsibility to notify both the local regulatory authority and other regulatory agencies about the safety of a study treatment under clinical investigation. The Sponsor will comply with country-specific regulatory requirements relating to safety reporting to the regulatory authority, IRBs/independent ethics committees, and Investigators.

Individual safety reports must be prepared for suspected unexpected serious adverse reactions according to local regulatory requirements and sponsor policy and forwarded to Investigators as necessary.

An Investigator who receives an individual safety report describing a serious adverse event or other specific safety information (e.g., summary or listing of serious adverse events) from the Sponsor will file it along with the IB and will notify the IRB, if appropriate according to local requirements.

Safety Monitoring Plan

Subject safety will be routinely monitored as defined in the Sponsor's safety surveillance and signal management processes.

Pregnancy and Lactation

Details of all pregnancies and/or lactation in female subjects will be collected after the start of study treatment and until 7 days after EOS. Details of all pregnancies in female partners of male subjects will be collected after the start of study treatment until 7 days after EOS.

If a pregnancy is reported, the Investigator is to inform Amgen within 24 hours of learning of the pregnancy and/or lactation and is to follow the procedures outlined in [Appendix 5](#). Amgen

Global Patient Safety will follow up with the Investigator regarding additional information that may be requested.

Abnormal pregnancy outcomes (e.g., spontaneous abortion, fetal death, stillbirth, congenital anomalies, ectopic pregnancy) are considered serious adverse events.

Further details regarding pregnancy and lactation are provided in [Appendix 5](#).

7.2.2. Clinical Laboratory Evaluations

Blood and urine samples will be collected for clinical laboratory evaluations (including clinical chemistry, hematology, urinalysis, and serology) at the times indicated in the Schedule of Assessments in [Appendix 8](#). Clinical laboratory evaluations are listed in [Appendix 2](#).

The Investigator is responsible for reviewing laboratory test results and recording any clinically relevant changes occurring during the study in CRF/eCRF. The Investigator must determine whether an abnormal value in an individual study subject represents a clinically significant change from the subject's baseline values. In general, abnormal laboratory findings without clinical significance (based on the Investigator's judgment) are not to be recorded as adverse events. However, laboratory value changes that require treatment or adjustment in current therapy are considered adverse events. Where applicable, clinical sequelae (not the laboratory abnormality) are to be recorded as the adverse event.

Subjects will be asked to provide urine samples for drugs of abuse screen and cotinine test, and will undergo an alcohol urine test at the times indicated in the Schedule of Assessments in [Appendix 8](#). For all female subjects, a pregnancy test and an FSH screen for postmenopausal women will be performed at the times indicated in the Schedule of Assessments in [Appendix 8](#).

An Investigator (or designee) will perform a clinical assessment of all clinical laboratory data.

7.2.3. Vital Signs

Supine BP, supine heart rate, respiratory rate, and oral body temperature will be assessed at the times indicated in the Schedule of Assessments in [Appendix 8](#). Vital signs may also be performed at other times if judged to be clinically appropriate or if the ongoing review of the data suggests a more detailed assessment of vital signs is required.

All measurements will be performed singly and repeated once if outside the relevant clinical reference range.

Subjects must be supine for at least 5 minutes before BP and pulse rate measurements. When vital signs are scheduled at the same time as blood draws, the blood draws will be obtained at the scheduled timepoint, and the vitals will be obtained as close to the scheduled blood draw as possible, but prior to the blood draw.

7.2.4. 12-lead Electrocardiogram

Resting 12-lead ECGs will be recorded after the subject has been supine and at rest for at least 5 minutes at the times indicated in the Schedule of Assessments in [Appendix 8](#). Single 12-lead ECGs will be repeated twice, and an average taken of the 3 readings, if either of the following criteria apply:

- QTcF is >500 ms
- QTcF change from the baseline (predose) is >60 ms.

Additional 12-lead ECGs may be performed at other times if judged to be clinically appropriate or if the ongoing review of the data suggests a more detailed assessment of ECGs is required. The Investigator (or designee) will perform a clinical assessment of each 12-lead ECG.

7.2.5. Physical Examination

A full physical examination or symptom-directed physical examination will be performed at the timepoints specified in the Schedule of Assessments in [Appendix 8](#).

8. SAMPLE SIZE AND DATA ANALYSIS

8.1. Determination of Sample Size

Approximately 14 subjects will be enrolled in order that approximately 12 subjects complete the study. The sample size for this study is based on studies of similar design and considered adequate for evaluation of the study objectives.

8.2. Analysis Populations

8.2.1. Pharmacokinetic Population

The PK population will include all subjects who received at least 1 dose of rosuvastatin or sotorasib and have evaluable PK data. A subject may be excluded from the PK summary statistics and statistical analysis if the subject has an adverse events of vomiting that occurs at or before 2 times median time to maximum concentration or diarrhea within 24 hours of dosing.

8.2.2. Safety Population

The safety population will include all subjects who received at least 1 dose of sotorasib or rosuvastatin and have at least 1 postdose safety assessment.

8.3. Pharmacokinetic Analyses

The plasma PK parameters of rosuvastatin on Days 1 and 6, and sotorasib on Day 6 will be calculated using standard noncompartmental methods.

The primary PK parameters are C_{max} , AUC_{last} , and AUC_{inf} for rosuvastatin on Days 1 and 6. All other PK parameters will be regarded as secondary and will not be subject to inferential statistical analysis. A linear mixed-effects model will be used to analyze log-transformed primary PK parameters. The model assumes fixed effect for treatment and a random effect for subject. Geometric mean ratios for C_{max} and AUC values and associated 90% confidence intervals (test/reference) will be estimated. The “reference” treatment for PK analysis will be rosuvastatin administered alone, while the “test” treatment will be rosuvastatin administered in combination with sotorasib.

Additional parameters may be calculated. Specific details will be presented in the Statistical Analysis Plan for this study.

8.4. Safety Analysis

The number and percentage of subjects reporting any adverse events will be tabulated by Medical Dictionary for Regulatory Activities system organ class and preferred term. Tables of fatal adverse events, serious adverse events, adverse events leading to withdrawal from investigational product or other protocol-required therapies, and significant treatment-emergent adverse events will also be provided. Subject-level data may be provided instead of tables if the subject incidence is low.

Endpoints for clinical laboratory tests, ECG, and vital signs will be summarized.

8.5. Interim Analysis

No interim analyses are planned for this study.

10. APPENDICES

Appendix 1: Safety Events: Definitions and Procedures for Recording, Evaluating, Follow-up, and Reporting of Adverse Events and Serious Adverse Events

Definition of Adverse Event

Adverse Event Definition

• An adverse event is any untoward medical occurrence in a clinical study subject irrespective of a causal relationship with the study treatment.• Note: An adverse event can therefore be any unfavorable and unintended sign (including an abnormal laboratory finding), symptom, or disease (new or exacerbated) temporally associated with the use of a treatment, combination product, medical device, or procedure.• Note: Treatment-emergent adverse events will be defined in the Statistical Analysis Plan (SAP).
Events Meeting the Adverse Event Definition

• Any abnormal laboratory test results (hematology, clinical chemistry, or urinalysis) or other safety assessments (e.g., electrocardiogram, radiological scans, vital signs measurements), including those that worsen from baseline, that are considered clinically significant in the medical and scientific judgment of the Investigator (i.e., not related to progression of underlying disease).• Exacerbation of a chronic or intermittent pre-existing condition including either an increase in frequency and/or intensity of the condition.• New conditions detected or diagnosed after study treatment administration even though it may have been present before the start of the study.• Signs, symptoms, or the clinical sequelae of a suspected drug-drug interaction.• Signs, symptoms, or the clinical sequelae of a suspected overdose of either study treatment or a concomitant medication. Overdose per se will not be reported as an adverse event/serious adverse event unless it is an intentional overdose taken with possible suicidal/self-harming intent. Such overdoses are to be reported regardless of sequelae.• “Lack of efficacy” or “failure of expected pharmacological action” per se will not be reported as an adverse event or serious adverse event. Such instances will be captured in the efficacy assessments. However, the signs, symptoms, and/or clinical sequelae resulting from lack of efficacy will be reported as adverse event or serious adverse event if they fulfill the definition of an adverse event or serious adverse event.
Events NOT Meeting the Adverse Event Definition

• Medical or surgical procedure (e.g., endoscopy, appendectomy): the condition that leads to the procedure is the adverse event.

- Situations in which an untoward medical occurrence did not occur (social and/or convenience admission to a hospital).
- Anticipated day-to-day fluctuations of pre-existing disease(s) or condition(s) present or detected at the start of the study that do not worsen.

Definition of Serious Adverse Event

A Serious Adverse Event is defined as any untoward medical occurrence that meets at least 1 of the following serious criteria:

Results in death (fatal)

Immediately life-threatening

The term “life-threatening” in the definition of “serious” refers to an event in which the subject was at risk of death at the time of the event. It does not refer to an event, which hypothetically might have caused death, if it were more severe. For instance, drug-induced hepatitis that resolved without evidence of hepatic failure would not be considered life-threatening even though drug-induced hepatitis can be fatal.

Requires in-patient hospitalization or prolongation of existing hospitalization

In general, hospitalization signifies that the subject has been detained (usually involving at least an overnight stay) at the hospital or emergency ward for observation and/or treatment that would not have been appropriate in the physician’s office or outpatient setting. Complications that occur during hospitalization are an adverse event. If a complication prolongs hospitalization or fulfills any other serious criteria, the event is serious. When in doubt as to whether “hospitalization” occurred or was necessary, the adverse event is to be considered serious. Hospitalization for elective treatment of a pre-existing condition that did not worsen from baseline is not considered an adverse event.

Results in persistent or significant disability/incapacity

The term “disability” means a substantial disruption of a person’s ability to conduct normal life functions. This definition is not intended to include experiences of relatively minor medical significance such as uncomplicated headache, nausea, vomiting, diarrhea, influenza, and accidental trauma (e.g., sprained ankle) which may interfere with or prevent everyday life functions but do not constitute a substantial disruption.

Is a congenital anomaly/birth defect

Other medically important serious event

Medical or scientific judgment is to be exercised in deciding whether serious adverse event reporting is appropriate in other situations such as important medical events that may not be immediately life-threatening or result in death or

hospitalization but may jeopardize the subject or may require medical or surgical intervention to prevent 1 of the other outcomes listed in the above definition. These events are typically to be considered serious.

Examples of such events include invasive or malignant cancers, intensive treatment in an emergency room or at home for allergic bronchospasm, blood dyscrasias, or convulsions that do not result in hospitalization, or development of drug dependency or drug abuse.

Recording Adverse Events and Serious Adverse Events

Adverse Event and Serious Adverse Event Recording

- When an adverse event or serious adverse event occurs, it is the responsibility of the Investigator to review all documentation (e.g., hospital progress notes, laboratory, and diagnostics reports) related to the event.
- The Investigator will then record all relevant adverse event/serious adverse event information in the Event electronic Case Report Form (eCRF).
- The Investigator must assign the following adverse event attributes:
 - Adverse event diagnosis or syndrome(s), if known (if not known, signs or symptoms)
 - Dates of onset and resolution (if resolved)
 - Did the event start prior to first dose of investigational product, other protocol-required therapies
 - Assessment of seriousness
 - Severity (or toxicity defined below)
 - Assessment of relatedness to the investigational product(s) and/or study-mandated procedures
 - Action taken
 - Outcome of event.
- If the severity of an adverse event changes from the date of onset to the date of resolution, record as a single event with the worst severity on the appropriate eCRF.
- It is not acceptable for the Investigator to send photocopies of the subject's medical records to Sponsor in lieu of completion of the appropriate eCRF page.
- If specifically requested, the Investigator may need to provide additional follow-up information, such as discharge summaries, medical records, or extracts from the medical records. In this case, all subject identifiers, with the exception of the subject number, will be blinded on the copies of the medical records before submission to the Sponsor.

- The Investigator will attempt to establish a diagnosis of the event based on signs, symptoms, and/or other clinical information. In such cases, the diagnosis (not the individual signs/symptoms) will be documented as the adverse event/serious adverse event.

Evaluating Adverse Events and Serious Adverse Events

Assessment of Severity

The Investigator will make an assessment of severity for each adverse event and serious adverse event reported during the study. The assessment of severity will be based on the Common Terminology Criteria for Adverse Events (CTCAE) grading scale. For the CTCAE grading scale version 5.0 or higher, refer to:
https://ctep.cancer.gov/protocolDevelopment/electronic_applications/ctc.htm.

Assessment of Causality

- The Investigator is obligated to assess the relationship between investigational product(s), protocol-required therapy, and/or study-mandated procedure and each occurrence of each adverse event/serious adverse event.
- Relatedness means that there are facts or reasons to support a relationship between investigational product and the event.
- The Investigator will use clinical judgment to determine the relationship.
- Alternative causes, such as underlying disease(s), concomitant therapy, and other risk factors, as well as the temporal relationship of the event to study treatment administration will be considered and investigated.
- The Investigator will also consult the Investigator's Brochure and/or Product Information, for marketed products, in his/her assessment.
- For each adverse event/serious adverse event, the Investigator must document in the medical notes that he/she has reviewed the adverse event/serious adverse event and has provided an assessment of causality.
- There may be situations in which a serious adverse event has occurred and the Investigator has minimal information to include in the initial report. However, it is very important that the Investigator always make an assessment of causality for every event before the initial transmission of the serious adverse event data.
- The Investigator may change his/her opinion of causality in light of follow-up information and send a serious adverse event follow-up report with the updated causality assessment.
- The causality assessment is 1 of the criteria used when determining regulatory reporting requirements.

Follow-up of Adverse Event and Serious Adverse Event

- The Investigator is obligated to perform or arrange for the conduct of supplemental measurements and/or evaluations as medically indicated or as requested by the Sponsor to elucidate the nature and/or causality of the adverse event or serious adverse event as fully as possible. This may include additional laboratory tests or investigations, histopathological examinations, or consultation with other health care professionals.
- If a subject is permanently withdrawn from protocol-required therapies because of a serious adverse event, this information must be submitted to the Sponsor.
- If a subject dies during participation in the study, the Investigator will provide the Sponsor with a copy of any post-mortem findings including histopathology.
- New or updated information will be recorded in the originally completed eCRF.
- The Investigator will submit any updated serious adverse event data to the Sponsor within 24 hours of receipt of the information.

Reporting of Serious Adverse Event

Serious Adverse Event Reporting via Paper Serious Adverse Event Report Form

- Facsimile transmission of the Serious Adverse Event Report Form (see [Figure 2](#)) is the preferred method to transmit this information.
- In rare circumstances and in the absence of facsimile equipment, notification by telephone is acceptable with a copy of the Serious Adverse Event Report Form sent by overnight mail or courier service.
- Initial notification via telephone does not replace the need for the Investigator to complete and sign the Serious Adverse Event Report Form within the designated reporting time frames.
- Once the study has ended, serious event(s) should be reported to Sponsor (regardless of causality) if the Investigator becomes aware of a serious adverse event. The Investigator should use the paper-based Serious Adverse Event Report Form to report the event.

Figure 2: Sample Serious Adverse Event Report Form

A 20200426 Covance Study# 8461525 Sotorasib (AMG 510)	Clinical Trial Serious Adverse Event Report – Phase 1–4 Notify Amgen Within 24 Hours of knowledge of the event			 New  Follow-up
--	---	--	--	--

Amgen (Sponsor) Safety US: Email: [contact] or [contact]					

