2. OBJECTIVES AND ENDPOINTS

2.1. Objectives

The primary objective of the study is:

- to determine the effect of sotorasib on the PK of rosuvastatin, and to assess the PK of rosuvastatin when administered alone, in healthy subjects.

The secondary objectives of the study are:

- to assess the safety and tolerability of sotorasib when coadministered with rosuvastatin, and rosuvastatin alone, in healthy subjects
- to assess the PK of sotorasib when coadministered with rosuvastatin.

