8.6. Safety and Tolerability Assessments

8.6.1. Adverse Events

All AEs will be coded using the Medical Dictionary for Regulatory Activities (MedDRA) Version 24.0 (or higher if a new version is issued during the study; see the DMP for more details). All AEs will be assigned a severity grade using Common Terminology Criteria for Adverse Events (CTCAE) Version 5.0 (or higher if a new version is issued during the study; see the protocol for more details).

A treatment-emergent adverse event (TEAE) will be defined as an AE that starts during or after dosing, or starts prior to dosing and increases in severity after dosing.

A treatment-related TEAE will be defined as a TEAE with a relationship related to the study treatment, as determined by the investigator.

All AEs will be listed. In addition to the data recorded in the database, the listings will include derived onset time and duration. Onset time will be calculated from the time of dosing for TEAEs only.

CONFIDENTIAL

The frequency of subjects with TEAEs and the number of TEAEs will be summarized for the following categories:

- TEAEs (overall, serious, leading to discontinuation, and leading to death) by treatment
- TEAEs by severity and treatment
- Treatment-related TEAEs (overall, serious, leading to discontinuation, and leading to death) by treatment
- Treatment-related TEAEs by severity and treatment

The frequency of subjects will be summarized separately for TEAEs and treatment-related TEAEs by the following:

- System organ class, preferred term, and treatment
- Preferred term and treatment

For the AE data the following rules will apply:

- For the derivation of treatment-emergent status (applicable to all AEs): If the start date/time of an AE is incomplete or missing, an AE will be assumed to not be a TEAE, unless the incomplete start date/time or the end date/time indicates an AE started after dosing.
- For the derivation of treatment-related status (applicable to TEAEs only): If the study treatment relationship for a TEAE is missing, a TEAE will be assumed to not be a treatment-related TEAE.

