- For the derivation of onset time (applicable to TEAEs only): If the start date/time of a TEAE is missing, onset time will not be calculated. If the start date/time of a TEAE is incomplete, where possible, the minimum possible onset time will be calculated and presented in '≥DD:HH:MM' format (eg, if the date/time of dosing is 01MAY2019/08:00 and recorded start date/time of a TEAE is 03MAY2019, then the minimum possible onset time will be calculated by assuming a TEAE started at the first hour and minute of 03MAY2019 [03MAY2019/00:00], thus will be presented as onset time ≥01:16:00 in the listing). If the start date of a TEAE is the same as the date of dosing but the start time of a TEAE is missing, an onset time will be presented as '≥00:00:01'. Any clock changes will be accounted for in the derivation.
- For the derivation of duration (applicable to all AEs): If the end date/time of an AE is missing, duration will not be calculated. If the start or end date/time of an AE is incomplete, where possible, the maximum possible duration will be calculated and presented in '≤DD:HH:MM' format (eg, if the start of an AE date/time is 01MAY2019/08:00 and its recorded end date/time is 03MAY2019, then the maximum possible duration will be calculated by assuming an AE ended at the last hour and minute of 03MAY2019 [03MAY2019/23:59], thus will be presented as

Page 18 of 23

duration ≤02:15:59 in the listing). Any clock changes will be accounted for in the derivation.

- For the calculation of TEAE summary statistics: If the severity of a TEAE is missing, that TEAE will be counted under the 'missing' category.
- For the calculation of TEAE summary statistics: If a subject experienced multiple TEAEs with the same preferred term for the same treatment, this will be counted as 1 TEAE for that treatment under the maximum severity recorded.

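### Appendix 1 keeps one worst grade per adverse event and no date of change, so for worst grades 2 to 4 its listed fields cannot show a worsening after a dose, which SAP 8.6.1 uses to define a TEAE

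*Protocol*

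**What the plan says.** **Recording rule.** Protocol Appendix 1, on recording adverse events, says that an event whose severity changes between onset and resolution is to be handled thus: "record as a single event with the worst severity on the appropriate eCRF". The attributes the investigator must assign include onset and resolution dates, a flag for start before the first dose, and one severity. Grade at onset, grade at a later dose and date of change are not listed.

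**Analysis rule.** Appendix 1 leaves the definition of a treatment-emergent adverse event (TEAE) to the SAP. SAP 8.6.1 has two limbs. An event qualifies if it begins during or after dosing, "or starts prior to dosing and increases in severity after dosing". The summaries include "TEAEs by severity and treatment". Where a subject has several TEAEs with one preferred term under one treatment, "this will be counted as 1 TEAE for that treatment under the maximum severity recorded".

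**Start of collection.** Protocol Section 7.2.1 collects non-serious events from enrollment. Appendix 8, footnote l, starts at the first study treatment on Day 1. Enrollment is the allocation of the subject number (Section 3.1), which comes before the first dose (Section 4.4).

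**Objective served.** A secondary objective is "to assess the safety and tolerability of sotorasib when coadministered with rosuvastatin, and rosuvastatin alone, in healthy subjects".

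**The concern.** The second limb of the TEAE definition compares severity before and after dosing. The recording rule reduces that comparison to one number, the highest grade over the whole event, without saying when it was reached. One stated rule therefore removes the input that another stated rule uses.

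The design makes this more than a formality. Each subject takes rosuvastatin alone on Day 1 and rosuvastatin with sotorasib on Day 6, and safety is described for each treatment. An event that begins on rosuvastatin alone and worsens once sotorasib is added is one that a by-treatment severity table ought to be able to show. An event that begins before any dose raises a more basic question, namely whether it is a TEAE at all.

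**Working it through.** The plan states no figure on this point, so there is none to reproduce. The check is whether the recorded fields determine the answer.

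**Inputs.** The fields come from Appendix 1 and the two-limb definition from SAP 8.6.1. The documents name the CTCAE scale without listing its grades; I assume grades 1 to 5, with 5 fatal.

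**Step 1: what one record can mean.** Take an event ongoing at a dose. Let a be its grade before the dose and b its highest grade after it. The record holds w = max(a, b). For w from 1 to 4, the number of pairs with maximum w is w² − (w − 1)² = 2w − 1. A worsening means b > a, so b = w and a lies between 1 and w − 1, which gives w − 1 pairs. For w = 5 the subject was alive at the dose, so a is at most 4 and b = 5.

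| Worst grade recorded | Possible pairs | Pairs that are a worsening | Decidable? |
|---|---|---|---|
| 1 | 1 | 0 | yes, not worsened |
| 2 | 3: (1,2), (2,1), (2,2) | 1 | no |
| 3 | 5 | 2 | no |
| 4 | 7 | 3 | no |
| 5 | 4 | 4 | yes, worsened |

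Onset date, resolution date and the first-dose flag can be identical for every pair within a row. These are counts of possible histories, not probabilities.

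**Step 2: does a finer model change the answer?** Splitting the history into onset grade, highest grade before the dose, grade at the dose and highest grade after it gives 1, 7, 23, 54 and 30 histories for worst grades 1 to 5. Grades 2, 3 and 4 still contain both answers, grade 1 only no worsening, and grade 5 only worsening. This holds whether worsening is judged against the grade at the dose or against the highest grade before it. The counts depend on the model; the conclusion does not.

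**Step 3: where the SAP uses the missing answer.**

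- *Case (a), onset before the Day 1 dose.* Under Section 7.2.1 a non-serious event that starts between enrollment and the Day 1 dose is collected. It is a TEAE only through the second limb, so at worst grade 2 to 4 its status cannot be derived. Under footnote l it would not be collected. Serious events are collected from consent in both places, so the mismatch does not concern them.
- *Case (b), onset after the Day 1 dose and ongoing at the Day 6 dose.* Onset lies in a window of 5 × 24 = 120 hours. The first limb already makes the event a TEAE. What cannot be derived is whether it worsened after the Day 6 dose. The SAP does not say how a TEAE is assigned to a treatment. Assuming assignment by onset, histories (1,2), (2,1) and (2,2) all appear as grade 2 under rosuvastatin alone. Read per period, (1,2) would be grade 1 under rosuvastatin alone and grade 2 under the combination.

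**Step 4: does another rule fill the gap?** SAP 8.6.1 has rules for incomplete start or end times, missing relationship and missing severity. It has none for an unknown time of worsening.

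**The case against.** **The SAP does not ask for a test at Day 6.** A reader might infer that the SAP requires worsening to be judged at the Day 6 dose, so that the recording rule breaks its TEAE definition for every event spanning that day. The text does not support this. It refers to dosing without saying which dose, the Appendix 1 flag is tied to the first dose, and every event in case (b) is a TEAE already. This stands, so case (b) is conditional on reading dosing per period. It does not touch case (a).

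**The tables need a maximum, and the record supplies one.** This stands in part. The maximum is over the whole event, while the counting rule works within a treatment. But the missing assignment rule is a gap in the SAP, not in Appendix 1. A reader might infer that effects of sotorasib will be shown under rosuvastatin alone. That follows only if assignment is by onset, which is an assumption.

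**The eCRF may hold more.** The SAP was written after review of the eCRF and uses event times, whereas Appendix 1 lists only dates. The Appendix 1 list may therefore be incomplete. This stands: the documents do not show that grade changes go uncaptured. The Appendix 1 sentence would still direct the site to one record at the worst grade.

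**Other safeguards exist.** All events are listed, with onset time for TEAEs and duration. Causality is assessed for "each occurrence of each adverse event/serious adverse event", with timing relative to treatment considered. Serious events have a narrative, laboratory and vital-sign data are summarized by timepoint, and Protocol Section 8.4 allows subject-level data instead of tables when incidence is low. These reduce the practical loss, but none is specified as a source for deriving worsening.

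**Conclusion.** The concern holds in a limited form. On the fields that Appendix 1 lists, worsening after a dose cannot be determined for an event ongoing at that dose with worst grade 2, 3 or 4. Worst grade 1 and fatal events are unaffected.

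In case (a) overall TEAE status is undecidable, provided collection runs from enrollment; Section 7.2.1 and footnote l must be reconciled. In case (b) overall status is secure. What is lost is attribution of a worsening to the combination, provided dosing is read per period. Display of the worst grade under rosuvastatin alone needs the further assumption of assignment by onset.

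The documents give no frequency. With about 14 healthy subjects, such events may be few. Only secondary descriptive safety tables are affected: the SAP plans no inferential safety analysis, and the listings and the primary pharmacokinetic analysis are untouched. Priority: minor.

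**What to change.** 1. **Appendix 1 and the eCRF instructions.** When an ongoing event increases in severity after a dose, record the new grade with its date and time, in a dated grade-change field or a linked record. If the eCRF already does this, change only the Appendix 1 sentence.
2. **SAP 8.6.1.** State that dosing applies per period, assign each TEAE or worsening to the most recent treatment, and count linked records once per treatment.
3. **Collection start.** Make Section 7.2.1 and Appendix 8, footnote l, agree on when non-serious events begin to be collected.

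The cost is about one sentence in Appendix 1 and the eCRF instructions, a few short statements in the SAP, and one aligned passage. No new assessment is needed, because subjects are confined from Day -1 to Day 11 and asked about their condition at least daily. The downside is one extra eCRF field or a few more linked records, which must not inflate the number of TEAEs; the counting rule in item 2 guards against that.
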